Flow chart 2I: Consequence of flow dysfunction detected by monitoring and surveillance

Monitoring reports

Surveillance flow measurements (only for patients allocated to the surveillance group)

Listing of reasons for:

- Flow dysfunction for reasons other than recorded in registration of flow dysfunction
- Decision by the study team not to act on low flow measurement (PROTOCOL VIOLATION)

Clinical indicators of flow dysfunction refer to the decision rules for interventions defined in the study protocol (used to send notifications to the study sites).

No significant findings on duplex ultrasounds is defined as the absence of hemodynamically significant stenosis AND no clinically significant stenosis as determined by multidisciplinary review.

Table 2J: Time between surveillance flow measurements

	Monitoring		Surveillance		P
Time between regular flow measurements	Median (IQR)	N	Median (IQR)	N	...
>6 weeks	%		%		...
Thrombosis during delay	-		%		
Time until confirmatory flow measurement for low flow	Median (IQR)	N	Median (IQR)	N	...
>1 week	%		%		...
Thrombosis during delay	-		%		

Statistical analysis: Mann-Whitney U-test comparing median time between monitoring and surveillance groups; Chi squared test for categorical variables.

Table 2K: Time between indication and intervention

	Monitoring (N=...)				Surveillance (N=...)				P
	Median (IQR)	N	>1 week	Thrombosis in waiting time	Median (IQR)	N	>1 week	Thrombosis in waiting time	
All cases			%	%			%	%	...
Indications									
Clinical indicators of flow dysfunction			%	%			%	%	...
Access flow <500 mL/min without clinical indicators of flow dysfunction	-	-	-	-			%	%	
Interventions									
Percutaneous interventions			%	%			%	%	...
Open surgical interventions			%	%			%	%	...

Interventions for thrombosis outside the waiting time for interventions for clinical indicators of flow dysfunction or access flow <500 mL/min (in the surveillance group) are excluded.

Statistical analysis: Mann-Whitney U-test comparing median time between monitoring and surveillance groups.

Table 2L: Time between intervention and subsequent randomization

	Monitoring		Surveillance		P
Time between intervention and assessment of clinical success	Median (IQR)	N	Median (IQR)	N	...
>4 weeks	%		%		...
Thrombosis during delay	%		%		...
Time between confirmation of clinical success and subsequent randomization ^a	Median (IQR)	N	Median (IQR)	N	...
>2 weeks	%		%		...
Thrombosis during delay	%		%		...

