Clinical indicators of flow dysfunction refer to the decision rules for interventions defined in the study protocol (used to send notifications to the study sites).

The threshold for mean dynamic venous pressure will be derived from ROC curve analysis (Figure 10-2)

Calculate sensitivity, specificity, positive predictive value, and negative predictive value.

Figure 6E: Receiver operator characteristic (ROC) curves for diagnostic accuracy of absolute access flow to predict (A) interventions for clinical indicators of flow dysfunction <30 days, (B) thrombosis <30 days, and (C) loss of vascular access <30 days

Calculate area under the curve with 95% confidence intervals.

Figure 6F: Receiver operator characteristic (ROC) curves for diagnostic accuracy of relative access flow compared to baseline to predict (A) interventions for clinical indicators of flow dysfunction <30 days, (B) thrombosis <30 days, and (C) loss of vascular access <30 days

Calculate area under the curve with 95% confidence intervals.

Figure 6G: Receiver operator characteristic (ROC) curves for diagnostic accuracy of mean dynamic venous pressure to predict (A) interventions for clinical indicators of flow dysfunction <30 days, (B) thrombosis <30 days, and (C) loss of vascular access <30 days

Calculate area under the curve with 95% confidence intervals.

Figure 6H: Scatterplot of (A) absolute access flow to mean dynamic venous pressure, and (B) relative access flow compared to baseline to mean dynamic venous pressure

Statistical analysis: Pearson correlation coefficient with 95% confidence interval

Table 6I: Table / Figure 6B: Reproducibility / Inter-session reliability of vascular access monitoring

	Inter-session reliability (Cohen's kappa)
	Next dialysis session
Clinical indicators of flow dysfunction	...
Physical examination	...
Weak or discontinuous thrill	...
High pitched or discontinuous bruit	...
Hyperpulsatile vascular access	...
Weak vascular access	...
No thrill or bruit	...
Recurrent problems during dialysis	...
Inability to achieve target blood flow	...
New cannulation problems	...
Prolonged bleeding	...
Unexplained fall in dialysis efficiency	...
Other findings at inspection	...
Aneurysm	...
Hand ischemia	...
Infection	...
Edema	...
Skin lesions	...
Hematoma	...

The next dialysis session should be within 7 days of the initial assessment.

Table 6J: Diagnostic accuracy of vascular access monitoring to predict clinically relevant stenosis

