	Duplex ultrasound or intervention			No significant findings on multidisciplinary review of clinical indicators of flow dysfunction		
	N	Intervention <30 days (true positive)	No stenosis on imaging <30 days (false positive)	N	No intervention for clinical indicators of flow dysfunction, thrombosis, or loss of vascular access <30 days (true negative)	Intervention for clinical indicators of flow dysfunction, thrombosis, or loss of vascular access <30 days (false negative)
Clinical indicators of flow dysfunction	...	%	%	...	%	%
Physical examination	...	%	%	...	%	%
Weak or discontinuous thrill	...	%	%	...	%	%
High pitched or discontinuous bruit	...	%	%	...	%	%
Hyperpulsatile vascular access	...	%	%	...	%	%
Weak vascular access	...	%	%	...	%	%
No thrill or bruit	...	%	%	...	%	%
Recurrent problems during dialysis	...	%	%	...	%	%
Inability to achieve target blood flow	...	%	%	...	%	%
New cannulation problems	...	%	%	...	%	%
Prolonged bleeding	...	%	%	...	%	%
Unexplained fall in dialysis efficiency	...	%	%	...	%	%

Clinical indicators of flow dysfunction refer to the decision rules for interventions defined in the study protocol (used to send notifications to the study sites).

The sum of the counts may not add up to the total event rate because patients may have more than one clinical indicator of flow dysfunction.

Table 7A: Success rate of vascular access interventions for flow dysfunction

	All patients (N=...)		Monitoring (N=...)		Surveillance (N=...)		P
Technical success (<30% residual stenosis) ^a	%	N	%	N	%	N	...
Clinical success							
Access flow >500 mL/min	%	N	%	N	%	N	...
Resolution of clinical indicators of flow dysfunction ^b	%	N	%	N	%	N	...
Functional vascular access ^c	%	N	%	N	%	N	...

^a Only for percutaneous interventions

^b Only for interventions for clinical indicators of flow dysfunction

^c Functional vascular access is defined as: cannulated with 2 needles for 6 dialysis sessions in 30 days with prescribed dialysis blood flow

Statistical analysis: Chi squared tests

Figure 7B: Kaplan-Meier curves of (A) primary patency (any access-related intervention), (B)

assisted primary patency, and (C) secondary patency after interventions for flow dysfunction

Include interventions that result in functional vascular access. Censoring after loss of primary patency. Statistical comparison between monitoring and surveillance groups with log-rank tests.

Table 7C: Success rate of vascular access interventions for thrombosis

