	All patients (N=...)		Monitoring (N=...)		Surveillance (N=...)		P
Percutaneous thrombectomy	%	N	%	N	%	N	...
Technical success ^a	%	N	%	N	%	N	...
Clinical success ^b	%	N	%	N	%	N	...
Recurrent thrombosis in 3 months	%	N	%	N	%	N	...
Open thrombectomy	%	N	%	N	%	N	...
Technical success ^a	%	N	%	N	%	N	...
Clinical success ^b	%	N	%	N	%	N	...
Recurrent thrombosis in 3 months	%	N	%	N	%	N	...
No thrombectomy	%	N	%	N	%	N	...
Vascular access loss in 30 days	%	N	%	N	%	N	...
Permanent central venous catheter	%	N	%	N	%	N	...
Temporary central venous catheter	%	N	%	N	%	N	...

^a Return of thrill and bruit

^b Successful hemodialysis with the vascular access after thrombectomy: cannulated with 2 needles with prescribed dialysis blood flow

Statistical analysis: Chi squared tests

Figure 7D: Kaplan-Meier curves of (A) primary patency (any access-related intervention), (B)

assisted primary patency, and (C) secondary patency after interventions for thrombosis

Include interventions that result in clinical success. Censoring after loss of primary patency. Statistical comparison between monitoring and surveillance groups with log-rank tests.

Table 8A: Duplex ultrasound core lab assessment^a

	All lesions ^b (N=...)	Intimal hyperplasia type (N=...)	Shrinking type (N=...)	No stenosis type (N=...)
Inner diameter stenosis (mm)	... + SD	... + SD	... + SD	... + SD
Outer diameter stenosis (mm)	... + SD	... + SD	... + SD	... + SD
Inner diameter reference vessel (mm)	... + SD	... + SD	... + SD	... + SD
Outer diameter reference vessel (mm)	... + SD	... + SD	... + SD	... + SD
Intimal hyperplasia rate (%)	... + SD	... + SD	... + SD	... + SD
Vascular constriction rate (%)	... + SD	... + SD	... + SD	... + SD
Stenosis rate (%)	... + SD	... + SD	... + SD	... + SD

^a For multiple stenosis, the most severe stenosis (i.e. highest PSV-ratio) is chosen.

^b Definitions according to Suemitsu et al. J Endovasc Ther 2025;32(5):1607-1613. No stenosis is defined as <50% stenosis rate and >2 mm inner diameter.

Table 8B: Duplex ultrasound findings (selection of duplex ultrasound assessments with available images of the stenosis and subsequent balloon angioplasty of the stenosis)

	Intimal hyperplasia type (N=...)		Shrinking type (N=...)		No stenosis type (N=...)		P
Access flow (mL/min)	... + SD	N	... + SD	N	... + SD	N	...
Diameter outflow vein (mm) ^b	... + SD	N	... + SD	N	... + SD	N	...
Stenosis		N		N		N	...
None	%	N	%	N	%	N	
Single	%	N	%	N	%	N	
Multiple	%	N	%	N	%	N	

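### Table 6J scores true positives by treatment and false positives by imaging, so the two columns are not complements and the predictive value of each clinical sign is not validly defined

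*SAP*

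**What the plan says.** The table is titled "Table 6J: Diagnostic accuracy of vascular access monitoring to predict clinically relevant stenosis" (SAP section 6). It does not say what makes a stenosis clinically relevant.

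The positive block has the denominator "Duplex ultrasound or intervention" and two outcome columns, "Intervention <30 days (true positive" and "No stenosis on imaging <30 days (false positive".

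The negative block covers signs with no significant findings at multidisciplinary review. Its error column is "Intervention for clinical indicators of flow dysfunction, thrombosis, or loss of vascular access <30 days (false negative", and its true-negative column is the exact opposite of that.

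The one note under the table on counts not adding up concerns patients with several clinical indicators, that is, the rows. It does not deal with overlap or gaps between columns.

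Flow chart 2I has a definition of negative imaging: "No significant findings on duplex ultrasounds is defined as the absence of hemodynamically significant stenosis AND no clinically significant stenosis as determined by multidisciplinary review". It is not referenced in Table 6J.

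**The concern.** A predictive value needs one reference standard, with every test-positive episode classed as condition present or absent. Here presence is judged by whether the patient was treated and absence by what imaging showed. Two kinds of episode then have no proper place:

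- **Stenosis on imaging, not treated within 30 days.** It counts in N but in neither column. Table 2K, which reports waiting time from indication to intervention, shows that delay is foreseen, though it gives no 30-day figure.
- **Treated, imaging negative.** It meets both labels. Table 3C classifies percutaneous interventions by stenosis as none, single or multiple, so the SAP expects that such procedures may occur.

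The indications differ as well. The false-negative column names the reasons for intervention that count; the true-positive column accepts an intervention without stating a reason. Thrombosis or access loss within 30 days is an event in the negative block but has no place in the positive block.

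The trial asks whether follow-up by clinical signs alone is safe, and this is the table that reports the accuracy of each sign. A reader could take the true-positive share as the chance that a sign reflects a stenosis. As labelled, it is the chance that a sign was followed by treatment.

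**Working it through.** Table 6J is an empty shell. There is no stated accuracy figure to reproduce, so the check is on the structure of the columns.

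**Cells.** Split the N worked-up episodes, assuming each has an imaging result, into:

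- a = stenosis, treated within 30 days
- b = no stenosis, treated within 30 days
- c = stenosis, not treated within 30 days
- d = no stenosis, not treated

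**Columns as labelled.**

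- True positive: TP = a + b
- False positive: FP = b + d
- TP + FP = a + 2b + d = N + b − c
- Share with stenosis = (a + c)/N
- TP/N − share with stenosis = (b − c)/N

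The columns divide N properly only if b = c = 0. If b = c > 0 they sum to N by coincidence.

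**Three answers from one row (invented numbers).** Take a = 60, b = 10, c = 5, d = 25, so N = 100.

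- TP = 60 + 10 = 70; FP = 10 + 25 = 35; sum = 105 = 100 + 10 − 5
- TP/N = 0.70, which is the treatment rate
- 1 − FP/N = 0.65, which is the stenosis rate, (60 + 5)/100
- TP/(TP + FP) = 70/105 = 0.67, which is neither

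**Range.** The SAP gives no shares. Assume N = 100, 60% or 80% with stenosis, 0 to 30% of stenoses untreated at 30 days, and 0 to 30% of episodes without stenosis treated.

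| | 60% stenosis | 80% stenosis |
|---|---|---|
| c (untreated stenosis) | 0 to 18 | 0 to 24 |
| b (treated, no stenosis) | 0 to 12 | 0 to 6 |
| TP = a + b | 42 to 72 | 56 to 86 |
| FP = b + d | 40 | 20 |
| TP + FP | 82 to 112 | 76 to 106 |
| TP/N | 0.42 to 0.72 | 0.56 to 0.86 |
| TP/(TP + FP) | 0.51 to 0.64 | 0.74 to 0.81 |
| TP/N minus stenosis share, points | −18 to +12 | −24 to +6 |

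With b = c = 0 every version agrees with the single-standard value, 0.60 or 0.80.

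**Comparison within the SAP.** The negative block of Table 6J and all cross-tables of Table 6D set an event against its absence (or, in the margins, a threshold against its opposite). Only the positive block of Table 6J does not.

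**The case against.** **The double count is a reading of short headers.** No rule tells the analyst to enter an episode twice. A natural reading is that treated episodes are true positives, and untreated episodes with negative imaging are false positives. Then FP = d, and the overlap goes. This is fair, and a reader who infers that the SAP instructs double counting goes too far. But the sum then becomes a + b + d = N − c, so the untreated stenosis is still unplaced, and TP/N still differs from the stenosis share by (b − c)/N.

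**Treated cases without stenosis may be rare.** Tables 8A to 8C do have a no-stenosis group: "No stenosis is defined as <50% stenosis rate and >2 mm inner diameter". But that is a core-lab class within a "selection of duplex ultrasound assessments with available images of the stenosis and subsequent balloon angioplasty of the stenosis", so those lesions were treated as stenoses, and nothing says Table 6J uses the core-lab call. The None row of Table 3C is not limited to interventions prompted by signs. Table 3A lists diagnostic angiography apart from interventions for flow dysfunction, so a negative angiogram alone need not count as an intervention. Under the Flow chart 2I definition, a lesion judged clinically significant at review would not be negative. All this limits the likely size of b; none of it affects c.

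**Clinically relevant may mean that it led to treatment.** Then the true-positive column is right, but the false-positive column has to be the absence of intervention within 30 days. On either meaning one column must change.

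**Unrelated procedures confirming a sign.** A reader might infer from the bare true-positive label that surveillance-group interventions for low flow would confirm signs. The SAP does not support this: Tables 2K, 3B and 8C define that indication as low flow without clinical indicators, so an episode with a positive sign falls outside it. Table 3B likewise puts aneurysm and infection under reasons other than flow dysfunction. What stands is that the column omits the indication that its counterpart states.

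**Conclusion.** The concern holds as a defect of definition. The positive block of Table 6J uses two reference standards, so the predictive value of each sign is not validly defined and is biased for stenosis whenever b and c differ. It rests on the column labels alone and needs no assumption about frequencies.

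It would be too strong to say that the accuracy reported is wrong: the shell reports none. Nor can a size or direction be given. The ranges above come from assumed shares and include zero. The discrepancy might even be visible in the finished table, because N and both percentages are shown, but the reader could not tell b from c, and equal values would hide each other.

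It would also be too strong to call this a main output. Section 5.1.2 lists the accuracy of flow measurements as a secondary outcome, not the accuracy of clinical signs, which appears only in this table. The table is exploratory in effect. The primary outcome and the safety analyses do not depend on it.

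**What to change.** Before analysis, state one reference standard for the positive block and make its columns mutually exclusive and exhaustive. Either of two forms would do:

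1. **Imaging standard.** True positive is a significant stenosis on duplex or angiography within 30 days, taken as the complement of the Flow chart 2I definition; false positive is no such stenosis, treated or not. Report treatment within 30 days in a separate descriptive column. The negative block would remain event-based, so the table should say that its halves use different standards. The 2I definition also keeps an element of multidisciplinary judgement.
2. **Event standard.** True positive is intervention for clinical indicators of flow dysfunction, thrombosis or access loss within 30 days; false positive is none of these. This matches the negative block. Show stenosis not treated and treated without stenosis as separate descriptive cells, and say in the title that the target is the event, because the sign itself helps to trigger treatment.

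In either form, limit intervention to the indications already named in the false-negative column.

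The cost is a change of table wording, since Tables 2N and 3C already plan to report the imaging findings. The downside is that a few episodes treated without prior imaging must be classified from the procedure angiogram.

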4.2.1. Inclusion criteria

In order to be eligible to participate in this study, a subject must meet all of the following criteria:

1. Adult patients aged 18 years or older
2. End-stage renal disease with unlikely recovery of kidney function according to the attending nephrologist
3. Arteriovenous fistula or arteriovenous graft as hemodialysis vascular access that fulfills both of the following criteria at the time of trial enrolment:
 - a. Maturation: access flow volume of at least 500mL/min; and
 - b. Functional: the vascular access was cannulated with 2 needles and achieved the prescribed access circuit flow in at least 6 dialysis sessions over the past 30 days. Patients who have single needle hemodialysis for reasons other than vascular access dysfunction (e.g. for nocturnal hemodialysis) but who can be cannulated with 2 needles for flow measurements and fulfil the other requirements for a functional vascular access can be enrolled as well.
4. Planning to remain in one of the participating dialysis centers for at least 1 year

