Interventions resulting in or from vascular access abandonment are excluded.

^a Only for interventions with clinical success.

Statistical analysis: Mann-Whitney U-test comparing median time between monitoring and surveillance groups; Chi squared test for categorical variables.

Table 2M: Duplex ultrasound for vascular access flow dysfunction - Available measurements

	Monitoring (... person-years)	Surveillance (... person-years)	Event rate ratio (95% CI)	P
Duplex ultrasound for clinical indicators of flow dysfunction ^a	N	N	... (...-...)	...
Duplex ultrasound for access flow <500 mL/min without clinical indicators of flow dysfunction ^a	N	N	... (...-...)	...
Duplex ultrasound not for flow dysfunction	N	N	... (...-...)	...

Statistical analysis: general linear mixed effect model with Poisson distribution and identity link, and with time as off-set variable (see Table 3A for details).

Table 2N: Findings of duplex ultrasound for flow dysfunction

	All patients (N=...)		Monitoring (N=...)		Surveillance (N=...)		P
Access flow (mL/min)	... + SD	N	... + SD	N	... + SD	N	...
Diameter outflow vein (mm) ^b	... + SD	N	... + SD	N	... + SD	N	...
Stenosis		N		N		N	...
None	%	N	%	N	%	N	
Single	%	N	%	N	%	N	
Multiple	%	N	%	N	%	N	
Stenosis characteristics ^c							
Location		N		N		N	...
Fistulas	%	N	%	N	%	N	...
Arterial inflow	%	N	%	N	%	N	
Juxta-anastomotic vein	%	N	%	N	%	N	
Outflow vein	%	N	%	N	%	N	
Graft	%	N	%	N	%	N	...
Arterial inflow	%	N	%	N	%	N	
Juxta-anastomotic arterial	%	N	%	N	%	N	
In graft	%	N	%	N	%	N	
Juxta-anastomotic venous	%	N	%	N	%	N	
Outflow vein	%	N	%	N	%	N	
Vessel diameter							
Stenosis (mm)	... + SD	N	... + SD	N	... + SD	N	...
Reference vessel (mm)	... + SD	N	... + SD	N	... + SD	N	...
Diameter reduction (%)	... + SD	N	... + SD	N	... + SD	N	...
Peak systolic velocity							
Stenosis (cm/s)	... + SD	N	... + SD	N	... + SD	N	...
Reference vessel (cm/s)	... + SD	N	... + SD	N	... + SD	N	...
PSV ratio	... + SD	N	... + SD	N	... + SD	N	...
Hemodynamic significance (yes)	%	N	%	N	%	N	...

^a Clinical indicators of flow dysfunction refer to the decision rules for interventions defined in the study protocol (and used to send notifications to the study sites).

^b Mean of diameter proximal / mid / distal outflow vein.

^c For multiple stenosis, the most severe stenosis (i.e. highest PSV-ratio) is chosen.

Statistical analysis: Chi squared tests for categorical variables and Student t-test for continuous variables

Table 2O: End of study

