Balloon inflation time (/min)	... (....-....)	...
Balloon inflation pressure (/atm)	... (....-....)	...
Paclitaxel-coated balloon (yes)	... (....-....)	...
Covered stent (yes)	... (....-....)	...
Luminal loss before treatment (/%)	... (....-....)	...
Luminal loss after treatment (/%)	... (....-....)	...

^a For multiple stenosis, the target lesion is the most severe stenosis (i.e. highest PSV-ratio with duplex ultrasound).

Statistical analysis: all variables will be entered into multivariable Cox regression models

Check for assumptions of statistical model: linearity, multicollinearity, independence of errors, and proportional hazards

Table 8F: Complications of percutaneous interventions

	Intimal hyperplasia type (N=...)		Shrinking type (N=...)		No stenosis type (N=...)		P
No complications	%	N	%	N	%	N	...
Extravasation after angioplasty	%	N	%	N	%	N	...
Balloon dilation	%	N	%	N	%	N	...
Covered stent	%	N	%	N	%	N	...
Other treatment	%	N	%	N	%	N	...
Bleeding from access site	%	N	%	N	%	N	...
Compression dressing	%	N	%	N	%	N	...
Thrombin injection	%	N	%	N	%	N	...
Surgical closure	%	N	%	N	%	N	...
Other treatment	%	N	%	N	%	N	...
Other complication	%	N	%	N	%	N	...

Statistical analysis: Chi squared tests

Table 9A: Cannulation practice – comparison between study groups

		All patients (... dialysis sessions)		Monitoring (... dialysis sessions)		Surveillance (... dialysis sessions)	P
Cannulation technique		N		N		N	...
Rope ladder	%	N	%	N	%	N	
Buttonhole	%	N	%	N	%	N	
Ultrasound-guided cannulation		N		N		N	...
No	%	N	%	N	%	N	
Cannulation site determination	%	N	%	N	%	N	
Ultrasound-guided puncture	%	N	%	N	%	N	
Needle position assessment	%	N	%	N	%	N	
Needle type		N		N		N	...
Steel	%	N	%	N	%	N	
Plastic	%	N	%	N	%	N	
Needle size		N		N		N	...
15G	%	N	%	N	%	N	
16G	%	N	%	N	%	N	
17G	%	N	%	N	%	N	
Other	%	N	%	N	%	N	
Single needle prescription	%	N	%	N	%	N	...
Cannulation difficulties ^a	%	N	%	N	%	N	...
Cannulation failure ^b	%	N	%	N	%	N	...
Arterial punctures		N		N		N	...
1	%	N	%	N	%	N	
2	%	N	%	N	%	N	
3 or more	%	N	%	N	%	N	
Venous punctures		N		N		N	...
1	%	N	%	N	%	N	
2	%	N	%	N	%	N	
3 or more	%	N	%	N	%	N	
Hematomas	%	N	%	N	%	N	...

^a> 1 attempt to place and secure two needles (or one needle for dialysis sessions with single needle prescription)

^binability to place and secure two needles (or one needle for dialysis sessions with single needle prescription)

Statistical analysis: Chi square tests

Table 9B: Cannulation practice – predictors of cannulation problems

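### Table 7A's definition of functional access omits the single-needle exception, so eligible single-needle participants would normally be scored as not functional after an intervention

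*SAP*

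**What the plan says.** Four places in the SAP bear on this point.

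- **Entry (section 4.2.1, criterion 3b).** A functional access needs two-needle cannulation at the prescribed circuit flow in at least 6 sessions over the past 30 days. An exception follows. It covers "Patients who have single needle hemodialysis for reasons other than vascular access dysfunction (e.g. for nocturnal hemodialysis) but who can be cannulated with 2 needles" when access flow is measured; if they "fulfil the other requirements for a functional vascular access can be enrolled as well", they enter the trial.
- **Success after an intervention for flow dysfunction (section 6, Table 7A, footnote c).** "Functional vascular access is defined as: cannulated with 2 needles for 6 dialysis sessions in 30 days with prescribed dialysis blood flow". There is no exception.
- **Success after thrombectomy (section 6, Table 7C, footnote b).** "Successful hemodialysis with the vascular access after thrombectomy: cannulated with 2 needles with prescribed dialysis blood flow". Again there is no exception, but also no session count and no time window.
- **Cannulation outcomes (section 6, Tables 9A and 9B).** Both tables carry a row for single-needle prescription, and their footnotes on difficulty and failure accept two needles "or one needle for dialysis sessions with single needle prescription".

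The Table 7A definition is used elsewhere. Figure 7B admits only interventions after which the access is functional. The sensitivity analyses listed under Tables 3A and 4A exclude patients with clinical failure and point to Table 7A for what that means.

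**The concern.** The SAP lets single-needle patients in and provides for them in the cannulation tables. It then judges their access after an intervention by a needle count that their prescription does not normally produce. Needle count is a fair marker of function in a patient prescribed two needles. In a patient on single-needle dialysis for another reason, such as nocturnal treatment, it reflects the prescription and says nothing about the access.

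A working access would then be recorded as not functional, its intervention would be missing from the post-intervention patency curves, and the patient could be removed from sensitivity analyses of the primary outcome and of serious adverse events. That last removal takes out the whole patient, with all events and follow-up. It can affect only patients who have had an intervention, and the two strategies are designed to differ in how often interventions occur, so the removals need not be balanced between arms.

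**Working it through.** The plan states no figure here to reproduce. The check compares definitions and makes one short count.

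**1. Are such patients in the analysed data?** Yes, by design. Criterion 3b admits them, and Tables 9A and 9B tabulate and model single-needle prescription. Table 2O counts transfer to single-needle nighttime dialysis during the trial as an end of study, so the point mainly concerns patients already on single needle at enrolment.

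**2. Can they meet Table 7A footnote c?**

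- Two-needle sessions required: 6 in 30 days (Table 7A, footnote c).
- Two-needle sessions foreseen: those for flow measurement (criterion 3b), done monthly (section 2.7), so about 1 in 30 days.
- Allowance for post-intervention, confirmatory or random repeat measurements (an assumption): about 1 to 4 in 30 days.
- Shortfall: 6 − 4 = 2 to 6 − 1 = 5 sessions.

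For scale, section 5.3 says participants are seen three times a week, which gives 3 × 30/7 ≈ 12.9 sessions in 30 days. Meeting the rule takes two needles in 6/12.9 ≈ 47% of sessions. Someone whose two-needle sessions are limited to flow measurements does not come near that.

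**3. What follows from failing the functional row?**

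| Place | Link to the definition | Effect |
|---|---|---|
| Table 7A, functional row | Direct | Scored as not functional |
| Figure 7B | Direct: functional access is the entry condition | Intervention left out of the curves |
| Clinical success (section 5.1.2, item 6) | Restored function is one of its joint parts; needles not mentioned | Fails if function is read from Table 7A |
| Sensitivity analyses, Tables 3A and 4A | Through the pointer to Table 7A | Patient excluded if the functional row decides |
| Primary analysis (section 5.2.1) | None | Unaffected |

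The other two clinical-success rows of Table 7A, on access flow and on resolution of clinical indicators, can still be met by these patients.

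**4. How large is the effect?** That needs the number of single-needle participants, their interventions and the underlying success rate. The SAP gives none of these, so no effect on the success rates can be computed.

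**The case against.** The strongest reply is that this is one footnote, feeding secondary output, for a group of unknown and perhaps small size. The rule is the same in both arms, and nothing shows that it favours either. That stands, and it limits the weight of the point.

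Other replies stand in part:

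- *The main text does not count needles.* Sections 5.1.2 and 5.2.1 describe clinical success and failure through restored function. On that wording a single-needle patient whose earlier function returns is not a failure. The effect on the sensitivity analyses therefore rests on the pointers to Table 7A and on how its rows are combined. It is conditional, unlike the effect on Figure 7B.
- *Some patients may have mixed prescriptions.* Table 9A records prescription by session, so a patient who often uses two needles could reach six. Failure is the normal result under the SAP's description, but it is not a certainty.
- *Criterion 3b permits enrolment and does not formally redefine a functional access, and Tables 9A and 9B concern a different outcome.* Both are true. The SAP nevertheless recognises that the two-needle requirement does not suit these patients, and Table 7A repeats it without saying why.

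A reader might also infer three stronger things that the SAP does not support:

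- *That Table 7C and Figure 7D fail these patients in the same way.* Table 7C footnote b sets no number of sessions and no window, so a single two-needle flow session at prescribed flow could satisfy it.
- *That these patients are barred from being randomised again.* Table 2L is a table of waiting times. Its footnote, "Only for interventions with clinical success", limits one row; it neither refers to Table 7A nor states a rule for repeat randomisation.
- *That the success rate is lowered by a particular amount.* Any such figure would rest wholly on an assumed share of patients and an assumed success rate.

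**Conclusion.** The point holds for Table 7A footnote c. As written, the rule misclassifies: a participant on single-needle dialysis at enrolment, for reasons other than access dysfunction, would normally be scored as not functional after an intervention even when the access works. Removal of the intervention from Figure 7B follows directly. Removal of the patient from the clinical-failure sensitivity analyses of Tables 3A and 4A follows where clinical failure is read from Table 7A, as those tables direct.

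This rests on two-needle sessions being limited to flow measurements, about monthly, and on repeat measurements not raising them to six in 30 days. The primary analysis is not affected. The size of the effect is unknown, and bias between the arms is possible but not shown. Table 7C has the same gap in wording without the same certain consequence.

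**What to change.** Reconcile Table 7A footnote c with criterion 3b by adding a clause such as: *or one needle for patients with a single-needle prescription for reasons other than access dysfunction*. The session count, the 30-day window and the prescribed blood flow stay as they are. State that this definition governs Figure 7B and the clinical-failure exclusions under Tables 3A and 4A. Add the same clause to Table 7C footnote b so that the two success tables agree.

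The restriction on the reason for single-needle use should stay in, so that a switch to one needle because the access is failing still counts as failure.

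The cost is one clause in each of two footnotes and a cross-reference. Single-needle prescription is already planned for Table 9A, and for patients on single needle at enrolment the reason is settled by eligibility, so no new data should be needed. The change aligns an analysis definition and alters no clinical rule.
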